### (b) Inclusion criteria

- i) Female and male adolescents of Hispanic immigrant origin, defined by at least one parent born in a Spanish speaking country of the Americas. Parent must understand Spanish given that parent sessions are delivered in this language. In past studies, over 99% of all Hispanic parents understood Spanish.
- ii) Adolescent between the ages of 12 – 16 years
- iii) Adolescent living with an adult primary caregiver who is willing to participate
- iv) Families must have broadband Internet access on a device, including (but not limited to) a smartphone, iPad, tablet, computer at their home or other location (e.g., school, library, etc.)

(c) Exclusion Criteria

- i) Families reporting plans to move out of the South Florida area during the study.
- ii) Families reporting that adolescent has been diagnosed with a developmental delay.

(d) Screening for Eligibility

Clinic staff will let the research team know between a day and two weeks before whether they have Hispanic youth ages 12 - 16 scheduled to come into the clinic and if so at what time. When the potentially eligible family checks in, the family will be moved to a small office space where the assessor and/or facilitator will be. The assessor and/or facilitator will screen parent and youth (separately) by asking parents pre-defined screening questions (i.e. the inclusion criteria). If the participant declines at any moment, verbal consent or assent will be asked for the participant to complete a brief questionnaire.

Additionally, we will do the following:

a) UM/Jackson patients (parents only) will receive a letter (hand delivered, e-mail and/or mail) from their physicians informing them about the study. This letter will inform participants that they will be receiving a call from research study personnel to see if they are interested in participating. Additionally, a phone number will be provided for the potential parent participant to contact research personnel.

b) Research study staff will request permission from each clinic to have access to their scheduling system. On a daily basis, research study personnel will access data on which individuals have a scheduled appointment. No health information will be available to research study staff, only whether there is an appointment scheduled. Study staff will screen these individuals, at the clinic, to see which meet criteria. Study staff will then go to waiting room to recruit those that meet criteria.

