- Frequency of (past 90-day) unprotected sex in Hispanic adolescents over time.
- STI incidence (specifically, the incidence of gonorrhea and chlamydia).

ii) Secondary:

- Improvements in family functioning over time (e.g. parent-adolescent communication, parental monitoring of peers).
- Frequency of unprotected sex will be partially mediated by improvements in family functioning over time.
- Reduction of STI incidence will be partially mediated by improvements in family functioning and decreases in unprotected sex over time.

(b) Safety endpoints

Not applicable.

10) **Procedures Involved**

(a) Study Design

This study tests the effectiveness of eHealth Familias Unidas Primary Care in preventing drug use, unprotected sexual behavior, and STIs in a universal sample of Hispanic youth, this study will use a randomized trial design with two levels of intervention (eHealth Familias Unidas Primary Care and prevention as usual) as the between subjects factor with five repeated measures assessments at baseline, 6, 12, 24, and 36 months post baseline as the within subject factor.

Once both primary care giver and adolescent have completed the consent/assent, they will complete the baseline assessment electronically. Once the baseline assessment is complete, they will be randomized to one of the two conditions: eHealth Familias Unidas Primary Care (experimental prevention as usual (control) Condition. Please see attached for consent/assent forms (in English and Spanish). All consent forms will be completed electronically. All confidential study participant information will be stored electronically in secure University of Miami systems.

i) eHealth Familias Unidas Primary Care

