## 12) Data Management\*

### (a) Data Analysis Plan and Power Analysis

**H1a:** *eHealth Familias Unidas Primary Care will be effective, relative to Care as Usual, in reducing the frequency of (past 90-day) drug use in Hispanic adolescents over time.*

This hypothesis will be analyzed using Latent Growth Modeling (LGM). Growth models can be expressed in terms that are identical to models using random coefficients regression, mixed models or multi-level models, where the first level fits each response in time to an individual-level growth model. The second level represents the condition effect on the slope of drug use. LGM analyses will test for differences in trajectories of drug use over the 5 assessment time points among the 2 conditions. As recommended by Raudenbush and Bryk, we will use 2-level analysis to determine whether the mean trajectories of drug use for eHealth Familias Unidas Primary Care and prevention as usual differ significantly over time. Data analysis for this hypothesis and all others will be conducted using Mplus (v 7.2).

Power. Mplus Monte Carlo simulation with 10000 replications was used to calculate the power for this hypothesis using a latent growth curve model framework with one covariate (i.e., condition assignment) and missing data. With 5 time points (0, 6, 12, 24 and 36 months) and assuming a 5% attrition rate at each assessment (also assuming equal sample size across both conditions), with 228 cases in each condition at baseline (or 185 at the final assessment timepoint in each condition), we have 80% power to detect a regression coefficient equal to 0.09 (effect size = 0.3) in the regression of the slope growth factor on intervention condition. This is considered slightly over a small (0.2) effect size.

**H1b:** *eHealth Familias Unidas Primary Care will be effective, relative to prevention as usual, in reducing the frequency of (past 90-day) unprotected sex in Hispanic adolescents over time.*

The analytic plan and power analysis for this hypothesis are similar to that of H1a.

**H1c:** *eHealth Familias Unidas Primary Care will be effective, relative to prevention as usual, in reducing STI incidence (specifically, the incidence of gonorrhea and chlamydia).*

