This hypothesis will be analyzed using a univariate logistic regression for the binary outcome, new diagnoses of STIs (Yes/No). STI incidence will be defined as a positive laboratory test result for a new chlamydia or gonorrhea infection at any of the four follow up assessment timepoints. In the analysis for this hypothesis, condition will predict STI diagnosis. The test of the hypothesis will be based on a Wald test comparing the intervention regression coefficient to its standard error. Additionally, the time of STI diagnosis will be included as a covariate in the logistic regression to test the robustness of the intervention's effect.

**Power.** According to CDC national statistics, the annual STI incidence rate is 3.16% for Hispanic adolescents aged 15 to 19. Thus, we expect the 3-year STI incidence rate in the control group to be approximately 9.2%. Using a one-sided Z test with pooled variance to test the difference between two independent proportions (assuming the same 5% attrition rate at each assessment timepoint), the study has over 80% power to detect a difference of 6.1% in STI incidence between the two conditions. This difference in proportions translates to an effect size of Cohen's  $h = 0.26$ , considered a small ( $h = 0.2$ ) to medium ( $h = 0.5$ ) effect size, according to Cohen (1988).

**H2a:** *Intervention effects on frequency of drug use will be partially mediated by improvements in family functioning over time.*

To test for mediation, we will use the "product of coefficients" test described by MacKinnon and colleagues, which is based on the distribution of the indirect effect of the intervention through the mediator (Cohen, 1988). This procedure tests whether the product of the coefficients from the intervention to the mediator (a) and from the mediator to the outcome (b) is significantly different from zero. Specifically, we will estimate paths between intervention and family functioning (a), and between family functioning and drug use (b). Because we have five time points, our first mediation analyses will fit bivariate growth curves for both family functioning and drug use and examine the role of the (latent) slope of family functioning on the slope of

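### H1c's stated power above 80% is for a one-sided pooled Z test; the planned Wald test has no stated sidedness or alpha, and the control risk comes from an older age band

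*Combined protocol and SAP*

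**What the plan says.** STI incidence is one of three primary endpoints in section 9(a). Section 12(a) gives its analysis and its only power statement.

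- **Analysis.** A logistic regression of any new diagnosis, counted "at any of the four follow up assessment timepoints", on condition. "The test of the hypothesis will be based on a Wald test comparing the intervention regression coefficient to its standard error". No sidedness is given, and the available documents state no significance level for any test.
- **Power.** "Using a one-sided Z test with pooled variance to test the difference between two independent proportions", with 5% attrition at each assessment, the plan reports power above 80% for a 6.1-point difference.
- **Number per arm.** H1c gives none. It refers to the same attrition as H1a, which is worked out "with 228 cases in each condition at baseline (or 185 at the final assessment timepoint in each condition".
- **Control risk.** The source is that "the annual STI incidence rate is 3.16% for Hispanic adolescents aged 15 to 19", which the plan carries to about 9.2% over three years. Section 5(b) sets entry at "Adolescent between the ages of 12 – 16 years", and section 10(a) plans "five repeated measures assessments at baseline, 6, 12, 24, and 36 months post baseline".

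**The concern.** The power figure and the decision rule refer to different tests. The choice of pooled Z or Wald matters little on the one-sided basis at the plan's rates. Sidedness matters a good deal. A Wald statistic between 1.645 and 1.960 in the favourable direction is positive at one-sided 5% and negative at two-sided 5%, and the plan does not say which reading decides a primary endpoint. If that is settled after results are seen, the conclusion can turn on the choice. The reader also cannot tell whether the chance of missing a true 6.1-point difference is about 20% or about 33%.

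The second matter is the control risk. A rate for ages 15 to 19 is applied to all three years for everyone, although some entrants spend part or all of follow-up below age 15. The plan makes no allowance for this and gives no reason for leaving it out.

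**Working it through.** **Inputs.** Annual rate 3.16%, control risk 9.2%, difference 6.1 points and attrition 5% per assessment (12(a), H1c); 228 per arm (12(a), H1a); entry age 12–16 (5(b)); follow-up to 36 months (10(a)). The 5% level is assumed, because none is stated.

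**The plan's own figures.**
- Control risk: 1 − (1 − 0.0316)³ = 0.0918, which agrees with 9.2%. Intervention risk: 9.2 − 6.1 = 3.1%. Relative reduction: 0.061/0.092 = 66.3%.
- Number per arm at 36 months: 228 × 0.95⁴ = 185.7. Upper bound if everyone with one follow-up counts: 228 × 0.95 = 216.6. No attrition: 228.
- Pooled Z by normal approximation, n = 185: mean proportion 0.0615; SE under no difference √(2 × 0.0615 × 0.9385/185) = 0.02498; SE under the alternative √((0.092 × 0.908 + 0.031 × 0.969)/185) = 0.02478. One-sided power = Φ((0.061 − 1.645 × 0.02498)/0.02478) = 78.9%. Exact binomial enumeration of the same test gives 81.1%. The plan's claim therefore reproduces on a one-sided 5% basis.

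**The planned test.** The Wald statistic is the log odds ratio divided by √(1/x₁ + 1/(n − x₁) + 1/x₀ + 1/(n − x₀)), where x₁ and x₀ are the event counts. Every pair of counts was enumerated at 9.2% v 3.1%. An arm with no events was counted as non-rejection; at these rates that has probability of only about 0.969¹⁸⁵ = 0.003.

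| Per arm | Wald, one-sided 5% | Wald, two-sided 5% |
|---|---|---|
| 185 | 79.7% | 67.0% |
| 216 | 85.6% | 75.4% |
| 228 | 87.3% | 78.0% |

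At 185 per arm the difference from 9.2% detectable with 80% power by the Wald test is 6.12 points one-sided and 6.89 points two-sided.

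**Age band (assumption-based).** Suppose entry ages are spread evenly from 12 to just under 17. Mean time before age 15 is (3²/2)/5 = 0.9 years of 3, or 30% of follow-up. Let the under-15 rate be a fraction f of 3.16%, and average 1 − (1 − 0.0316)^y × (1 − 0.0316f)^(3−y) over entry ages, where y is the years spent at 15 or older. Wald power at 185 per arm, with the 66% relative reduction held:

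| f | Control risk | One-sided 5% | Two-sided 5% |
|---|---|---|---|
| 0 | 6.5% | 63.5% | 46.0% |
| 0.5 | 7.8% | 72.4% | 57.1% |
| 1 | 9.2% | 79.7% | 67.0% |

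If the absolute 6.1 points are held instead, power rises: at a control risk of 8.0%, one-sided Wald power is 84.7% and two-sided 73.5%. That requires a relative reduction of 0.061/0.080 = 76%. The rise does not continue to the bottom of the range. At a control risk of 6.5% the intervention arm would expect only 0.004 × 185 = 0.74 events, and the Wald test loses power there.

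**The case against.** The plan discloses its one-sided basis openly, in the same block of text as the Wald test, and H1c is worded as a reduction. One can fairly read the Wald test as one-sided too, in which case its power at 185 per arm is 79.7%, practically the stated figure. If everyone with at least one follow-up counts, it is 85.6% and the plan is conservative. All of this stands.

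A reader might infer that the power was miscalculated. It was not: the figure reproduces.

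A reader might also infer that the plan contradicts itself because its other tests are two-sided. H1a asks whether the trajectories for the intervention and "prevention as usual differ significantly over time", which has no direction although H1a is also phrased as a reduction. This shows that directional wording of a hypothesis does not by itself adopt a one-sided rule. It does not make the H1c test two-sided, since H1a is a different model. The text is silent, and every two-sided figure above is conditional.

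On age, a reader might infer that the trial is shown to be underpowered. The documents do not support that. Entrants aged 12 to 16 are 15 to 19 at month 36, so the rate suits the end of follow-up. No under-15 rate is given, and the effect on power changes direction with the quantity held fixed. Sexual activity reported in the face-to-face effectiveness study in section 4(b) does not settle the control risk either: it comes from a school sample, with intermittent 90-day windows and a different length of follow-up.

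**Conclusion.** The point holds as incomplete specification. The stated power is right for the test it names, but it is not tied to the test that will decide H1c. At an assumed 5% level and the plan's rates, the Wald test has about 80% power one-sided and 67.0% two-sided at 185 per arm. Two-sided, it stays below 80% even with no attrition (78.0%). The age mismatch is a fact of the documents, but its size is not. Under the stated assumptions control risk lies between about 6.5% and 9.2%, and one-sided Wald power at 185 per arm between about 63% and 80% if the relative reduction is held. This should be fixed, because it concerns a primary endpoint and can be settled now without cost to the conduct of the trial.

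**What to change.** In section 12(a), H1c:

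1. State alpha and sidedness for the Wald test before results are seen, with a reason if one-sided.
2. Replace the claim of power above 80% with the power of that Wald test and the number per arm it assumes. At 185 per arm this is about 80% if one-sided 5%, or about 67% with a detectable difference of about 6.9 points if two-sided 5%.
3. Say that 9.2% derives from ages 15 to 19, and show power over a range of lower control risks labelled as assumed, stating whether the relative or the absolute difference is held.

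The cost is a few sentences and a less favourable power statement. Enrolment, data and procedures do not change.

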Youth's and parents' own drug use will be measured using items used as part of the Monitoring the Future survey (Johnston et al., 2010). This 47-item self-report instrument assesses lifetime drug use and the frequency of drug use (by type of drug) in the 3 months prior to assessment. Additionally, questions regarding the use of e-cigarettes and hookahs for lifetime use, the previous 90 days and previous 30 days will be asked. CRAFFT (10 items) will assess the consequences of alcohol and drug use. Finally, three questions regarding second hand smoking will be asked:

*How much do you think you are exposed to tobacco smoke at home?"  
(select one: not at all, somewhat, moderately, a lot, extremely  
How much do you think you are exposed to tobacco smoke outside of  
home?" (select one: not at all, somewhat, moderately, a lot, extremely  
How many years in total did you live in the same household with someone  
else who smoked tobacco products?"*

The Klein Sexual Orientation measure (adolescents only, 8 items) will be used to assess adolescent sexual orientation and preferences.

Vancouver Index of Acculturation (VIA; parents and adolescents, 20 items) will be used to assess acculturation and practices.

The CES-D (parents and adolescents, 20 items) will be used to assess symptoms of depression.

ACES (for parents only, 17 questions) will assess adverse events before the age of 18 for parents

The CASA (for parent and adolescent, 8 items) will assess use of community services.

Four items (adolescent only) have been incorporated to evaluate experiences with bullying.

The Revised Behavior Problem Checklist (RBPC; parent only, 55 items): the externalizing subscales of the RBPC will be used to assess adolescent problem behaviors from the parent perspective.

The externalizing subscales of the Youth Self Report (YSR; adolescent only, 32 items) will be used to evaluate adolescent problem behaviors from the adolescent perspective.

Health related quality of life (QOL; parent and adolescent, six items) will be used to examine physical, mental and emotional health.

CRAFFT (adolescent, 10 items): assesses the consequences of alcohol and drug use.

Five questions have been created to assess participant understanding of the consent form.

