drug use. The product of the two pathways  $(a) \times (b)$  is the indirect effect of eHealth Familias Unidas Primary Care to drug use through the family functioning trajectory. As noted above, we will be testing whether the product  $(a) \times (b)$  is statistically significantly different from zero, by comparing the observed value of  $(a) \times (b)$  to the empirical distribution calculated using the bias-corrected bootstrap. In addition to this long-term developmental mediation model, we will also test if the initial changes in family functioning from baseline to the 6 month follow-up mediate the effect of intervention on drug use trajectory. Our team has expertise in conducting mediational analyses in multilevel models.

Power. Mplus Monte Carlo simulation with 10000 replications was used to calculate the power for this hypothesis using a mediation model framework. With a final sample size of 370 (assuming 5% attrition rate at each assessment timepoint), we have 80% power to uncover a significant mediating effect when the regression coefficient of pathways 'a' is approximately -0.36 and 'b' is approximately -0.18 (i.e.,  $R^2$  effect size were 0.033 for the relationship between X and M (i.e., path 'a;') and M and Y (i.e., path 'b'), which is considered a small effect (Cohen, 1988).

***H2b: Intervention effects on frequency of unprotected sex will be partially mediated by improvements in family functioning over time.***

The analytic plan and power analysis for this hypothesis are similar to that of H1b.

***H2c: Intervention effects on STI incidence will be partially mediated by improvements in family functioning and decreases in unprotected sex over time.***

We will use MacKinnon's method described in H1b with the exception that the outcome for this hypothesis is binary. The Weighted Least Squares Means and Variance adjusted (WLSMV) estimator in Mplus will be used to estimate the indirect effect. With WLSMV, a continuous latent response variable ( $y^*$ ) underlying the observed dichotomous variable is used to test for the mediated or indirect effect.

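### H2a–H2c test mediation through a path that randomisation does not protect, with no baseline confounder and no sensitivity analysis named for it

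*Combined protocol and SAP*

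**What the plan says.** Section 12(a) of the combined protocol and SAP, under H2a, uses the product-of-coefficients approach: "This procedure tests whether the product of the coefficients from the intervention to the mediator (a) and from the mediator to the outcome (b") differs from zero. The paths are then named: "Specifically, we will estimate paths between intervention and family functioning (a), and between family functioning and drug use (b"). Two models are planned. The first fits growth curves to both variables over the five assessments, to "examine the role of the (latent) slope of family functioning on the slope of" drug use. The second asks whether "initial changes in family functioning from baseline to the 6 month follow-up mediate the effect of intervention on drug use trajectory". The reference distribution is "the empirical distribution calculated using the bias-corrected bootstrap".

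Only condition, family functioning and drug use appear in these models. No baseline covariate, no assumption about unmeasured confounding and no sensitivity analysis is stated. H2b says only that its plan resembles H1b, which contains no mediation method. H2c also points to H1b, changes the outcome to binary with the WLSMV estimator, and adds unprotected sex as a mediator.

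Plausible common causes are nevertheless measured. Section 10(c) lists age, marital status and family income, parental adverse childhood events and externalising scales. Of youth and parents it says that their "own drug use will be measured using items used as part of the Monitoring the Future survey", and "The CES-D (parents and adolescents, 20 items) will be used to assess symptoms of depression". Section 10(b) says that follow-up repeats the baseline data collection, so baseline values will exist.

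**The concern.** Random assignment makes the arms comparable, which protects path a and the H1 comparisons. It does not make families with improving functioning comparable with families whose functioning does not improve. Parental depression or drug use, for example, could slow improvement in family functioning and also speed the rise in youth drug use. The two slopes would then be associated even if family functioning had no effect on drug use, and path b would absorb that association in the hypothesised direction. With a real path a, the product a × b can be significant for the wrong reason, and a larger sample makes this more likely.

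Three of the six hypotheses concern mechanism. At stake is whether the trial can say that the programme works through family functioning.

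**Working it through.** **Inputs.** Section 12(a), H2a: final N = 370, a ≈ −0.36, b ≈ −0.18, R² = 0.033 per path, power 80%. Section 12(a), H1c: 9.2% control STI incidence and a detectable difference of 6.1 points. Alpha is not stated for mediation; two-sided 0.05 is assumed, since the test asks whether the product "is statistically significantly different from zero, by comparing the observed value of" a × b with its distribution. Signs are dropped below. The confounder strength r is an assumption throughout.

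**The plan's own figures.** Attrition: 456 × 0.95⁴ = 371.4, consistent with 370 (2 × 185). In a simulated single-mediator model, power at the design values is 73–78% with the delta-method test (78.5% at exactly R² = 0.033, unit total variances and no direct path), about 86% with a product-distribution interval, and about 90% with the planned bias-corrected bootstrap. The stated 80% is therefore within 2 points of a delta-method calculation, and the single-mediator model is a fair frame for the plan's coefficients.

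**Bias.** Let X be condition and U a standardised baseline confounder:

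- M = aX + rU + √(1−r²)·e₁
- Y = bM + rU + √(1−r²)·e₂

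Given X, Var(M) = 1 and Cov(M, rU) = r². If U is omitted, the estimate of b centres on b + r². With b = 0 the spurious value is 0.04, 0.09 and 0.16 at r = 0.2, 0.3 and 0.4. It equals the whole design value at r = √0.18 = 0.42. With true b = 0.18 the estimate centres on 0.22 at r = 0.2 and 0.27 at r = 0.3.

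**Approximate check by hand.** The chance that both paths are significant:

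- Path a: z = (0.36/2)·√370 = 3.46, power 0.933.
- Path b at r = 0.3: z = 0.09·√370/√(1−0.09²) = 1.74, power 0.412.
- Product: 0.933 × 0.412 = 0.38.

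The same steps give 0.05, 0.11 and 0.82 at r = 0.1, 0.2 and 0.4.

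**Simulated rate of declaring mediation when b = 0 (a = 0.36, N = 370)**

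| r | Single mediator, product or Monte Carlo interval | Same, adjusted for U | Single mediator, bias-corrected bootstrap | Same, adjusted | OLS slope-on-slope, slope reliability 0.8 |
|---|---|---|---|---|---|
| 0.1 | 5% | 4% | not run | not run | 5% |
| 0.2 | 11% | 5% | 18% | 8% | 7% |
| 0.3 | 36–38% | 4–5% | 47% | 6% | 22% |
| 0.4 | 79–80% | 5% | 85% | 8% | 60% |

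The bootstrap columns rest on 400 replications of 500 resamples. With no confounding at all, that test rejected 8.5%, so its excess over 5% after adjustment belongs to the test and not to leftover confounding.

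The last column estimates each family's slope by least squares at 0, 6, 12, 24 and 36 months and lets U drive both slopes. Reliability 0.8 is assumed. Adjustment there gives 3–4%. A hand check multiplies b by 0.8 and a by √0.8. At r = 0.4, path a has z = 0.36·√0.8/2·√370 = 3.10 (power 0.872), and path b has z = 0.128·√370/√(1−0.128²) = 2.48 (power 0.699). The product is 0.61. At reliability 0.5 the simulated rates are 5%, 9% and 19% at r = 0.2, 0.3 and 0.4.

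**Two conditions that switch the problem off.** If U shifts only the starting levels, the slope-on-slope rate stays near 4–5%. If a = 0, the product interval rejects at most about 5%, even at r = 0.5.

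**Events for H2c.** Intervention incidence at the detectable difference: 9.2 − 6.1 = 3.1%. Events: 0.092 × 185 + 0.031 × 185 = 17.0 + 5.7 ≈ 23.

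**The case against.** The strongest reply is that the planned model is a growth model. Stable family differences go into the intercept factors, and a confounder that acts only on levels does no harm. This stands. The single-mediator rates should not be read as the error rates of H2a. The bias needs a factor that drives both rates of change, and a correlation of 0.3–0.4 with both slopes is a stronger assumption than the same correlation with levels. The growth model reduces the problem but does not remove it.

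Four stronger readings are tempting, and the documents do not support them:

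- A reader might infer that baseline family functioning and baseline drug use are left out. They are not: baseline is the first point of both growth curves, and the second H2a model uses change from baseline.
- A reader might infer that any shared cause produces a significant indirect effect. At r = 0.1 the rate is about 5%.
- A reader might infer that H2b and H2c specify unadjusted mediation models. They point to a section with no mediation method, so the absence of covariates there is silence through a cross-reference.
- A reader might infer that the efficacy claims are at risk. The H1 comparisons are between randomised arms.

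It is also fair to say that a long covariate list would be unsafe for H2c. With about 23 events, eight covariates plus condition and two mediators are 11 parameters, or about two events each.

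**Conclusion.** The point holds in a limited form. Path b is observational, and the plan neither adjusts it nor tests how far confounding could explain it, although relevant baseline measures are collected. If path a is real, as the plan expects, a factor that drives both slopes can produce a mediation finding when b is zero.

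The direction of this argument is secure; its size is not. In the closer analogue it ranges from negligible (about 5% at r = 0.1) to serious (about 60% at r = 0.4), under assumed confounder strength and slope reliability. That analogue is a least-squares approximation to the latent growth model. H2c was not simulated; the same reasoning applies to its binary outcome, but no rate is claimed. This is a cheap improvement to the mechanism analyses.

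**What to change.** In section 12(a):

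- **H2a and H2b.** Write the mediation model out for H2b instead of referring to H1b. Regress the mediator and outcome slope factors, and the baseline-to-6-month change mediator, on a fixed set of baseline covariates already collected: for example age, family income, parent drug use, parent and youth CES-D, and externalising score. Handle baseline family functioning and baseline outcome by regressing slopes on the intercept factors. Do not enter the time-0 scores again as predictors, since they are already growth indicators. Keep condition in the outcome equation as the direct path.
- **H2c.** State the method in full. Use a very small covariate set or one summary score, and describe the result as exploratory.
- **All three.** Report how large a residual mediator–outcome correlation would remove the indirect effect, and give the unadjusted model as a sensitivity analysis.

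The cost is SAP wording and more complex models; no new data are needed. Adjustment does not deal with unmeasured confounders or with the two slopes running over the same period, which is why the residual-correlation analysis is needed as well.
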